1. INTRODUCTION

1.1. Background

The history of fecal microbiota therapy and its success

Fecal microbiota transplantation (FMT) has been employed in the treatment of gastrointestinal disorders in humans since 1958, when it was first described by Eiseman to treat fulminant pseudomembranous enterocolitis.(1) Over the last several years, investigators have reported their experiences on over 300 patients who have received fecal microbiota therapy for treatment of *Clostridium Difficile* infection (CDI). (2) This 2012 meta-analysis reviewed over 27 studies using FMT for the treatment of refractory and often fulminant CDI associated colitis with an overall success rate of 92%. A more recent study on the treatment of CDI published in the New England Journal of Medicine was halted prematurely due to the overwhelming success of patients randomized to FMT for CDI as compared to standard antibiotic therapy. (3) Interestingly, Hamilton and colleagues have recently demonstrated that a frozen inoculum from a "universal screened donor" is equal in efficacy for CDI to a "fresh" donation from such an individual (90% vs. 92%; not significantly different). (4,5) They also note that the frozen approach allows for rigorous donor screening in a cost effective manner. Taking into account its well-documented clinical efficacy, apparent cost savings and safety, FMT for CDI, despite its unconventional nature, is now considered standard-of-care therapy. Research has recently shown oral frozen inoculum is non-inferior to colonoscopically delivered frozen donor FMT in treating recurrent CDI (6), thereby reducing substantial risks and costs associated with colonoscopic delivery of FMT.

The use of fecal microbiota therapy in inflammatory bowel disease (IBD), a natural next-step

IBD is a difficult to treat, chronic inflammatory disease, currently without a cure. IBD often requires life-long immune suppression and, at times, surgical intervention to keep under control. Even our most robust medical therapies are expensive, lack universal clinical efficacy, and are rife with significant risk of infection, malignancy and drug reactions. Given the strong microbial influence in the proposed etiopathogenesis of IBD, FMT has been used for the treatment of IBD in both children and adults for over a decade. Borody and colleagues pioneered the use of FMT in IBD as published in their initial case series in 2003, including six patients all of whom achieved a clinical remission following FMT. (7) A more recent retrospective meta-analysis reviewed 17 articles including 41 patients with IBD receiving FMT, many of whom also had CDI. (8) In patients treated for their IBD, the majority experienced a reduction of symptoms (19/25), cessation of IBD medications (13/17) and disease remission (15/24). While suggesting potential promise of FMT for the treatment of IBD, these heterogeneous retrospective reports are difficult to interpret.

Early evidence supports multiple FMT's

Early data suggests single administration of FMT may be inferior to multiple doses of FMT given over time. Vermeire prospectively delivered FMT by naso-jejunal tube over two days in 4 adult patients who suffered from refractory CD. While they reported no long-term

adverse effects, this group saw only temporary clinical response and microbial change in the gut ecosystem of these patients. (9) Kump found similar tolerability and safety in treating 6 Ulcerative colitis (UC) patients with a single FMT delivered colonoscopically but only temporary clinical improvement in some of the underlying IBD activity (11). Similarly, he reported no long-term engraftment of donor microbiota on recipient. Research has showed no apparent adverse events in 3 pediatric patients with IBD (2 of whom had CD) treated by single FMT all delivered colonoscopically for the primary indication of recurrent CDI but no improvement in underlying IBD clinical status. (12)

Multiple FMT administration seems to show more promising results. An adult case report by Kao showed complete resolution of severe Crohn's colitis after 2 colonoscopically delivered FMT's separated by 1 month with significant alterations/engraftment in the patient's gut microbial profile after FMT. (13) Similarly, Vandenplas reported improvement and eventually complete remission of infantile severe IBD activity with multiple FMTs from 2 separate donors over time. (14) Kunde and colleagues recently published a larger prospective safety and tolerability study of daily FMT enemas for 5 days in 10 children with IBD showing it was safe and well tolerated. (9) Seven of nine (78%) of subjects showed clinical response within 1 week, six out of the nine (67%) of subjects maintained clinical response at 1 month, and three out of the nine (33%) subjects achieved clinical remission at 1 week after FMT. In a large double-blind placebo controlled trial, Moayeddi suggests that 16/27 (60%) patients had subjective improvement of underlying UC activity after 6 weekly FMT therapies delivered by fecal retention enema. One third of these patients who showed initial subjective clinical response to an initial course of FMT eventually went into remission if FMT administration was maintained for a longer period of time. (15)

Best Mode of Delivery

There remains much uncertainty about the "best" mode of delivery of FMT. The most promising, prospective research using FMT for IBD to date utilized FMT delivery by retention enema (Moayeddi and Kunde, in adult and pediatric patients, respectively). Daily enema therapy for IBD colitis is routine in clinical standard practice for delivery of topical steroid and aminosalicylate therapy. Indeed, even in fragile, very sick adult populations with multiple co-morbidities and recurrent C. diff infection, where FMT is life-saving but any procedure is dangerous, FMT by retention enema is considered the safest and least invasive FMT delivery method available with minimal to no procedurally associated risk. Therefore, enema or colonoscopy represents the "traditional" method by which to perform FMT.

In the pediatric population, we are considerate of the invasive nature of enema therapy and the potential associated risks of anxiety and discomfort. An oral delivery would be an attractive, low risk and non-invasive alternative method of delivery for FMT therapy in this patient population. Based on our recent work in treating recurrent CDI successfully with oral inoculum by nasogastric tube delivery (16) and also by encapsulated oral inocula (work completed under FDA IND 15-199), the oral route of FMT seems to be non-inferior and obviates the need for persistent invasive delivery method. Vandenplas' case report showing ultimate remission of infantile IBD after 7 FMT (6 by an upper gastrointestinal delivery

route) provides "proof-of-concept" that this method of FMT delivery in a pediatric population is feasible, and potentially helpful in the treatment of IBD.

No studies to our knowledge have been done on FMT for pediatric IBD using frozen inocula collected from a universal donor. One might argue that given the known similarities of one's microbiome to their parents, a universal donor is more likely to introduce a more desirable commensal inoculum. (17,18) Moreover, given the frequency of IBD and other autoimmune conditions in first-degree relatives, it is common that a suitable healthy donor cannot be identified and an unrelated donor is required.

To best reflect and duplicate previous successes documented in the literature, we envision a hybrid FMT delivery method, using both FMT enema induction and an innovative oral encapsulated inoculum thereafter. We believe initial engraftment with donor stool is of paramount importance for eventual success of FMT therapy.

Fecal Microbiota Transplant (FMT) as a therapy for Ulcerative Colitis

Ulcerative Colitis (UC), a chronic inflammatory bowel disease (IBD) of the colon has similar strong microbial drivers of inflammation to CDI. FMT has been studied as a therapy for IBD in a number of small case series over the last three decades. (7,9,19) We propose that FMT would be a safe and well-tolerated therapy for pediatric UC. We further hypothesize that subjects will demonstrate subjective measures of clinical improvement (i.e., in the Pediatric Ulcerative Colitis Activity Index), in patient related outcome variables such as abdominal pain and number of daily bowel movements, as well as in objective inflammatory biomarkers.

1.2. Rationale

Profiling studies of the intestinal microbiome have associated the pathogenesis of IBD to characteristic shifts of the intestinal microbiota, reinforcing the view that IBD results from altered interactions between intestinal gut microbiota and the mucosal immune system. It is known that the microbial community in IBD patients is less diverse; enriched in Gammaproteobacteria and invasive E. coli species; and deficient in Faecalbacterium prauznitzii, certain Clostridia, Bacteroidetes, and Firmicutes. Metabolically, there is increased oxidative stress in these individuals, decreased presence of short chain fatty acids and metabolites of short chain fatty acids, increased auxotrophy, sulfate transport, amino acid transport, and toxin secretion. (20)

Recent pediatric work in multiple immunomodulator-refractory acute severe colitis has shown promising results in treating ill IBD children successfully with aggressive antibiotic regimens. Seven of 15 (47%) of this retrospective cohort of patients achieved complete remission with only alteration of their microbial community via aggressive multiple antibiotic regimens. (21)

It is entirely reasonable to assume that repopulating the gut habitat with healthy bacteria may alter disease activity course and progression. It is also entirely reasonable to assume

depleting gut flora with broad-spectrum antibiotic would be beneficial in setting the stage for appropriate transplant engraftment.

2. OBJECTIVES

2.1. Primary Objective

The primary aim of this phase I/II, randomized, placebo controlled study is the assessment of safety and tolerability of universal donor FMT compared to placebo in pediatric and young adult subjects (ages 5 years through 30 years) with Ulcerative Colitis, who have failed, are intolerant to, or have refused first-line maintenance therapy.

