4. STUDY TREATMENT

4.1. Investigational Agent

4.1.1. Fecal Microbiota Transplant (FMT) and placebo

The investigational agent consists of screened-donor inoculum of a biologically active human substance (FMT). FMT will be administered using either frozen screened-donor liquid stool (the investigational agent) in the form of retention enema (60 mL total for ages 5-10 and up to 120 mL total for ages greater than 10) or frozen capsules. Placebo will be administered using either placebo liquid or placebo capsules (both consisting of cocoa butter, glycerol, and brown food coloring). Donor material and placebo material will be obtained from Microbiome Health Research Institute (OpenBiome), a stool bank affiliated with the MIT-Broad Institute. All donors will be thoroughly screened for health and infectious status. (Cross ref. **BB-MF 15543**).

If randomized to FMT Arm, subjects will be matched with a specific stool donor and will then receive FMT induction enemas and FMT capsules containing this stool for the 8 week randomized portion of the trial. From each donor, sufficient stool to complete the study will be secured by OpenBiome and stored at their facility under appropriate storage conditions. The 8 week supply of the donor's inoculum will be maintained on-site at BCH and stored in accordance with supplier specifications and investigational agent guidelines. If subjects are eligible for open-label FMT and have previously been randomized to FMT, every effort will be made to use the same donor if possible. It is conceivable that enough stool to continue through open-label FMT treatment period(donors move or may become ineligible for stool donation) will not be practicably available and another appropriate donor may be selected for open-label FMT use if necessary.

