4.1.4. Blinding and Randomization

The first ten eligible subjects will be randomized in a 1:1 ratio according to a pre-determined block randomization procedure to receive either FMT or placebo. If safety allows, the remaining cohort of 50 eligible subjects will be randomized in a 1:1 ratio according to a pre-determined block randomization procedure to receive either FMT or placebo. An unblinded pharmacist or delegate will maintain the randomization list ensuring subjects are randomized appropriately and dispensed the correct treatment. The investigator, research personnel and study subjects will be blinded to treatment assignments.

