4.1.5. Drug Related Risks

Theoretically, there is a small potential of transmission of an unknown pathogen when delivering human donor fecal material to a recipient. Additionally, there is potential concern that the recipient might have an allergic reaction to a food component in donor stool that they might not be aware of and the donor has not avoided. There is also a potential that certain disease states might be inherently related to the gut microbial environment and a donor's risk for disease might be transmitted to a recipient. These risks will be mitigated by carefully screening donors for health status as well as relevant (known) infectious pathogens.

The literature to date comprises 100's of cases of FMT for CDI as well as for IBD. To date, no serious adverse events have been reported. Both Vermeire and Vandenplas reported systemic symptoms of fevers and abdominal pain in refractory IBD patients after FMT that resolved within 24-48 hours without intervention. (10,14) Pierog at Columbia University reported the development of granulomatous appendicitis two weeks after FMT for the indication of recurrent CDI in a pediatric patient with underlying ileocecal granulomatous Crohn's disease, but there is no clear reason to assume FMT is responsible for this otherwise Crohn's related outcome. (23) Quera reported a repeated sepsis episode with multi-drug resistant E. coli in a 61 year old male ill Crohn's patient treated by FMT for recurrent CDI who had had several episodes of similar bacteremia previous to FMT. (24) [name] reported a case of a 37 year old man who self-administered FMT at home for his ulcerative colitis who subsequently developed CMV colitis. (25) Additionally, De Leon reported a case of a patient who experienced a transient flare of ulcerative colitis that had been quiescent for twenty years after FMT for recurrent CDI. (26)

Retention enema is likely low-risk but may be less effective in some patients with inability to retain the FMT inoculum or placebo rectally. Mild discomfort and distress with anal manipulation are possible, though enemas are routinely used in our clinical practice to treat distal IBD colitis as well as constipation. Indeed in adult populations with advanced age, multiple comorbidities or limited life expectancy, this delivery mode is preferable. (27)

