6. SAFETY ASSESSMENT

6.1. Adverse Event Assessment and Reporting

Comprehensive assessments of any apparent adverse event(s) (AE) experienced by the study subject will be performed throughout the course of the study.

The PI will submit reports of unexpected Serious adverse events (SAEs) and other unanticipated problems to the Institutional Review Board (IRB) at Boston Children's Hospital and to OpenBiome according to their policies.

The PI will report events that are both serious and unexpected and that are associated with FMT/study intervention to the FDA and other applicable health authorities within the required timelines as specified in 21 CFR 312.32 (IND Safety Reports).

The following unexpected AEs will be assessed, recorded and reported to the Data Safety Monitoring Board (DSMB) on an expedited basis: all SAEs, AEs grade 3 (according to CTCAE 5.0 (31) if applicable) or above, and any unexpected AEs grade 2 or above that is possibly or probably related to FMT (as determined by a blinded investigator). Only an AE that meets the above criteria will be recorded and reported. Each reported AE will be described by its duration (i.e., start and end dates), regulatory seriousness criteria if applicable, expectedness, suspected relationship to the study treatment, and actions taken (a blinded investigator will determine expectedness, severity and relationship to study treatment).

Individual subject participation will be temporarily halted until the DSMB determines appropriateness of re-initiation of therapy in any subject experiencing an adverse event resulting in: an Emergency Department visit that is possibly or probably related to FMT, significant worsening of their disease, or experiences 1 SAE Grade \geq 3.

Individual subject participation in the study will be permanently stopped if a SAE Grade ≥ 3 is deemed possibly or probably related to FMT, including any hospital admission.

If 2 or more subjects experience 1 SAE grade \geq 4, all study activities will be halted until the DSMB determines appropriateness of re-initiation of therapy in any subject.

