7. STATISTICAL CONSIDERATIONS

7.1. Power Calculation

The primary aim of this phase I/II study is to establish whether or not FMT is a safe treatment for children and young adults with UC. Based on clinical experience, adverse events (AEs) in IBD patients are common and include abdominal pain, cramping, diarrhea, fever, bloody stool, vomiting, frequent defecation, joint pain, and eye pain. It's estimated that 70% of patients in any given year will experience a flare of their disease and have some or a combination of these symptoms. Safety, therefore, needs to be assessed relative to the high prevalence of AEs in this population. For the primary outcome, we will take any new reported SAEs or worsening of the existing AEs during the study period following enrollment into account.

The study will be powered for equivalence in the proportion of new SAEs or worsening of the existing AEs, assuming null (Ho) and alternative (Ha) hypotheses defined as follows:

$$\begin{split} & \text{Ho: } p1-p2 \leq \text{-}\delta_L \ \text{ or } p1-p2 \geq \delta_U. \\ & \text{Ha: } \delta_L \leq p1-p2 \leq \delta_U \end{split}$$

where p1 is the proportion of new SAEs or worsening of the existing AEs in the placebo group, p2 is the proportion in the FMT group, δ_L is the lower margin and δ_U is the upper margin. We expect to enroll a total of 60 patients into this study for a total of 30 FMT and 30 placebo patients. Assuming the rate of new incident SAEs or worsening of existing AEs in the placebo group is 10%, there will be 82% power to reject Ho that the difference in proportions is 0.20 or greater from zero in the same direction. Similarly, we will have an 85% power to reject a difference of 0.25 or greater if the rate of new incident SAEs or worsening of existing AEs increases to 15%.

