7.3. Data Analysis

All patients who are eligible, randomized, and have received at least one-dose of the study medication including antibiotics/placebo in the first week will be included into the analysis for primary outcomes to assess the safety and tolerability of FMT, as this will be a per protocol (and not intent-to-treat) analysis . Continuous variables will be presented as mean and standard deviation (SD) or median and interquartile range (IQR), depending on the distribution of the data. Categorical variables will be presented as number and percentage. Disease severity (PUCAI) and patient characteristics at baseline will be compared between the treatment groups to determine whether or not randomization resulted in balanced groups. Methods of 2-group comparison will include Student's t-test, the Mann-Whitney test, Pearson chi-square test, and Fisher exact test, depending on the distribution of the variable under consideration. The primary outcome of safety will be assessed via a 2×2 cross-tabulation, where the proportion of patients with new incident SAEs or upgrade of existing AEs in the FMT group will be compared to the proportion in the placebo group. Two one-sided tests for equivalence (32) will be constructed and the overall *P* value taken to be the larger of the lower and upper tests. Statistical significance will be assessed at *P*<0.05.

For the second outcome, we will use longitudinal data analysis methods to investigate changes in inflammatory biomarkers including stool calprotectin, stool lactoferrin, serum ESR/CRP, albumin, and hematocrit over the study period. Generalized Estimating Equations will be performed to examine the association between FMT and changes in these biomarkers.

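### Safety events are neither monitored nor analysed by donor, so harm confined to one donor's recipients is diluted in the FMT arm average

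*Combined protocol and SAP*

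**What the plan says.** - **Aim (2.1).** The trial sets out to assess the "assessment of safety and tolerability of universal donor FMT compared to placebo in pediatric and young adult subjects". The claim concerns a class of product, not particular donors.
- **Donor assignment (4.1.1).** Each subject in the FMT arm is matched to one donor for the 8 blinded weeks. The section adds: "From each donor, sufficient stool to complete the study will be secured by OpenBiome". For open-label use a different donor may be substituted. Neither the number of donors nor the number of recipients per donor is given.
- **Hazards (4.1.5).** The first named is that "there is a small potential of transmission of an unknown pathogen when delivering human donor fecal material to a recipient". Food components in the stool and transmission of a donor's own disease risk follow. The mitigation named is donor screening.
- **Event records (6.1).** "Each reported AE will be described by its duration (i.e., start and end dates), regulatory seriousness criteria if applicable, expectedness", followed by relationship to treatment and actions taken. Donor and lot are not on the list.
- **Monitoring (6.1, 6.2, 7.2).** The halting rules, DSMB review and two-stage rule count subjects without regard to donor. Unexpected SAEs and unanticipated problems also go to the stool bank under its policies.
- **Analysis (7.3).** The event proportion "in the FMT group will be compared to the proportion in the placebo group" in one 2×2 table, with two one-sided tests (TOST) for equivalence. No donor term appears.
- **Size (7.1).** "We expect to enroll a total of 60 patients into this study for a total of 30 FMT and 30 placebo patients". No allowance is made for donors.

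Donor does enter the plan on the benefit side, through donor and recipient biomarkers (2.2) and engraftment (5.3.3).

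**The concern.** The hazards that the plan lists first would appear as a cluster of events among recipients of one donor. The planned comparison averages over all FMT subjects, so a cluster is mixed with the results of unaffected recipients. Nothing in the plan gives the DSMB a count by donor. A donor-specific problem could therefore go unrecognised as such, both during the trial and in the final report, although the information needed to see it is already held: the match must be known in order to dispense, and the pharmacy logs dispensing by subject (4.1.2).

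A second question is whether sharing a donor makes FMT recipients' outcomes correlated, so that a test assuming independence declares equivalence too often.

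**Working it through.** **Inputs from the documents.** 30 per arm; placebo event rate 10% with margin 0.20, or 15% with margin 0.25 (7.1); TOST at P<0.05 (7.3).

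**Inputs assumed, because the documents give none.** The number of donors, the within-donor correlation (ICC), and the event rate under a harmful donor.

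**1. The plan's own power figures.** With equal rates p in both arms, one-sided power = Φ(margin/√(2p(1−p)/30) − 1.645).
- p = 0.10, margin 0.20: Φ(0.20/0.0775 − 1.645) = Φ(0.937) = 82.6% (stated 82%).
- p = 0.15, margin 0.25: Φ(0.25/0.0922 − 1.645) = Φ(1.067) = 85.7% (stated 85%).

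Both figures treat all 30 FMT subjects as independent. They are also powers of a single one-sided test. The full TOST, 2Φ(·) − 1, gives 65.1% and 71.4%. That is a separate matter, but it is the baseline for step 5.

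**2. Dilution.** Four near-equal donors supply 7, 7, 8 and 8 subjects. One donor's 8 recipients have a 50% event rate; the other 22 FMT subjects and all 30 placebo subjects have 10%. The FMT arm mean is (8×0.50 + 22×0.10)/30 = 6.2/30 = 20.7%, so the true arm difference is 0.107, while that donor's excess is 0.40. Exact enumeration gives:

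| Comparison | Share of trials |
|---|---|
| FMT v placebo, Fisher P<0.05 | 9.6% |
| That donor's 8 v the other 52, Fisher P<0.05 | 70.7% |
| Same, at 0.05/4 = 0.0125 | 46.2% |
| Wald TOST, margin 0.20, declares equivalence | 24.4% |

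For comparison, the TOST declares equivalence in 67.4% of trials when no donor is harmful, and in 26.0% when all 30 FMT subjects share the same 20.7% risk.

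**3. False equivalence if donors are a sample from a wider pool.** Take placebo at 10% and mean FMT at 30%, exactly on the margin. FMT events are beta-binomial within donor, and the Wald TOST is unadjusted. With no donor effect the rate is 5.4%.

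| Donors | ICC 0.05 | ICC 0.10 | ICC 0.20 |
|---|---|---|---|
| 2 | 9.7% | 13.3% | 18.6% |
| 4 | 7.5% | 9.5% | 12.8% |
| 10 | 6.1% | 6.7% | 8.0% |
| 30 (no sharing) | 5.4% | 5.4% | 5.4% |

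**4. The same boundary with the donors used held fixed.** The arm mean is again 30% in each case.
- 15 recipients at 50% and 15 at 10%: 4.2%.
- 10 at 70% and 20 at 10%: 2.8%.
- 8 at 50% and 22 at 22.7%: 4.9%.

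None exceeds the 5.4% found with no donor effect.

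**5. Cost of adjusting the test.** The design effect 1 + (30/K − 1)×ICC, with K donors, is applied to the FMT arm only (10% rate, margin 0.20). TOST power falls from 65.1% to:
- 57.0% with 5 donors, ICC 0.05 (effective FMT n = 30/1.25 = 24.0);
- 38.2% with 3 donors, ICC 0.10 (30/1.9 = 15.8);
- 26.3% with 2 donors, ICC 0.10 (30/2.4 = 12.5).

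**The case against.** **Sharing is not stated outright.** The sentence on securing enough stool could mean enough for one matched subject's course. This stands as a limit on size: with 30 donors there is no clustering. But the universal-donor wording implies sharing, and a plan that leaves the number open cannot rule it out.

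**The assumed values have no source in the documents.** True of the ICCs and of the 50% rate. Section 7.1 describes the expected events largely as background IBD symptoms, for which no donor correlation is shown. The figures are illustrations.

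**Controls exist.** Two subjects with SAEs of grade 4 or above halt the study whichever donor they had. Serious and grade 3 or higher unexpected events go to the DSMB on an expedited basis, and the stool bank, whose policies we cannot see, receives unexpected SAEs. A reader might therefore go too far in inferring that nobody would ever look at donor. What the documents do show is that none of these routes gives the DSMB a by-donor count, and that non-serious grade 2 events, which belong to the primary outcome in 5.3.3, would not routinely reach the stool bank.

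**The pooled test does react.** Declared equivalence drops from 67% to 24% in the harmful-donor example. This also stands: the signal is weakened and cannot be located, but it is not erased.

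**The 71% presumes that the bad donor is known.** Correct; the 46% is the fairer figure for a search over four donors.

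**Conclusion.** The gap is real: the plan links each subject to a donor and names donor-borne hazards, but plans no safety monitoring or analysis by donor. Under the assumed four-donor case the arm comparison detects the harm in about 10% of trials, against 46% to 71% for a by-donor comparison.

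Two stronger readings are tempting and are not supported.
- **That the 24% is false equivalence.** The true arm difference in that example is 0.107, inside the 0.20 margin, so the alternative hypothesis in 7.1 is true. A homogeneous arm with the same mean gives 26%. The weakness lies in what an arm average can show, not in the error rate.
- **That the type I error exceeds 5% whenever donors differ.** It rises only if donors are shared, outcomes correlate within donor, and the conclusion is meant to reach beyond the donors used. Then it goes from 5.4% to about 6–8% with 10 donors and 10–19% with 2, at ICC 0.05–0.20. With the donors treated as fixed it does not rise. The 5.4% starting value is itself a feature of the Wald approximation.

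This is a cheap improvement to the plan, not a reason to reject the primary test.

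**What to change.** **Sections 6.1 and 6.2.** Have the unblinded pharmacist supply donor and lot for each dose to the DSMB statistician, and tabulate adverse events by donor in the closed report. Keep donor off site forms so that blinding holds. What to do about any pattern stays with the DSMB.

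**Section 7.3.** Report the number of donors, the recipients per donor, and event proportions by donor with exact intervals. If there are enough donors, add a TOST that allows for donor clustering in the FMT arm only, as a sensitivity analysis. It should not be a veto on the primary result: with 2 to 4 donors the between-donor variance rests on 1 to 3 degrees of freedom, and the loss of power in step 5 of the working is large. With few donors, describe the results by donor and limit the conclusion to the donors studied.

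**Cost.** Some added wording and one extra closed table, built from the donor match and the dispensing logs that the trial already keeps. By-donor intervals will be wide: 0 events in 8 recipients still allows a rate up to 1 − 0.025^(1/8) = 37%, so a clean table is weak reassurance.
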